13.3 Sample Size and Power Calculations

We have used data from the belatacept phase II and DIRECT studies and from the literature (Grewal and Blake 2005) to provide expected values for the GFR standard deviations shown in Table 10 below. Sample size calculations for these analyses were performed using NCSS-PASS software.

In the primary endpoint analysis, we will compare the mean GFR between the study groups at 12 months. With the sample sizes fixed, a priori, at 30 subjects in each of the two treatment arms, the following table shows the smallest treatment mean GFR differences (i.e. effect sizes) we will be able to declare significantly different, with 80% power and Type I error rates of 0.05 and 0.10:

Table 11 - Smallest Detectable Difference in GFR at 12 Months for Different Standard Deviationsand Alpha Levels

GFR Standard Deviation	Alpha Level	Smallest Detectable Difference in GFR (mL/min/1.7 m ²)
16	0.05	12.0
	0.10	10.5
20	0.05	15.0
	0.10	13.0
24	0.05	18.0
	0.10	16.0

This study has been powered to be able to detect minimum detectable differences in the primary endpoint at both the 0.05 and 0.10 levels that are clinically relevant as shown in Table 9 above. When reporting results of the primary endpoint analysis, we will report a p-value as significant at the 0.10 level if it is less than 0.10 and as significant at the 0.05 level if it is less than 0.05. As previously stated, all secondary endpoint analyses will be performed at the 0.05 level.

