In addition, any subjects in the experimental arm of the study will transition from a protocol directed study therapy regimen to a physician directed clinical immunosuppressive regimen. The clinical immunosuppressive regimen may include belatacept and if so, the subject may continue to receive the study supply of belatacept until study completion on August 31, 2016.

B. Informed Consent

The investigator at each site must inform all active subjects that any further low dose CNI withdrawal has been halted and that each subject in the experimental arm will be transitioned from a protocol directed study therapy regimen to a physician directed clinical immunosuppressive regimen. The site investigator or designee must explain during the re-consent process the reason for the premature discontinuation of study therapy and describe in lay terms to the subject and/or the subject's legal representative what is involved in the transition from a protocol mandated therapy regimen to a physician directed clinical immunosuppressive regimen as well as the remaining study follow-up. The subject and/or the subject's legal representative, must read, sign, and date the informed consent form prior to any study-specific procedures.

A copy of the informed consent must be given to the subject and/or the subject's legal representative. The subject and/or the subject's legal representative will be informed that participation in the follow-up portion of the study is voluntary and that he/she may withdraw from the study at any time, for any reason.

C. Description of Amendment Modifications

No further subjects in the experimental arm of the study will undergo low dose CNI withdrawal. In addition, subjects in the experimental arm will transition from the protocol directed study therapy regimen to a physician directed clinical immunosuppressive regimen. If the subject, in conjunction with their treating physician,

opts to remain on belatacept after being reconsented regarding the new findings, they may receive the study supply of belatacept until study completion on August 31, 2016.

Subjects will continue to be followed until study completion based on the existing schedule they are following in Appendices 2, 3 or 4.

D. Drug Accountability

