10.4 Study Treatment Assignment Procedures

10.4.1 Blinding and/or Randomization

This is a randomized, open label study. Subjects will be randomized in an unblinded fashion to one of the two study groups in a 1:1 ratio using a web-based randomization system. The randomization schedule will not incorporate stratification variables. However, due to concerns about the potential for un-blinded investigators to be biased in their assessments of endpoints, all data analyses and reports and all data cleaning activities will be blinded with respect to treatment prior to end-of-study database lock, except for safety data reviews by the DSMB. The study treatment assignments will be blinded to all mechanistic core laboratory personnel, including the core pathologist.

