13.2 Endpoint Assessments

13.2.1 Primary Clinical Endpoint

The primary endpoint will be the week-52 eGFR. Mean eGFR of the belatacept group will be compared to the mean eGFR of the tacrolimus reference group within a mixed models repeated measures (MMRM) framework , wherein repeated measures of eGFR at weeks 4, 12, 28, 36 and 52 will be modeled as a linear function of time (and perhaps other baseline covariates) in the 2 treatment groups. At week-52, a contrast will be made between the eGFR mean of the belatacept group and the eGFR mean of the tacrolimus group. ANCOVA assumptions will be evaluated graphically via standard residual analyses. If the assumptions fail, a suitable transformation (e.g., natural logarithms) will be found and the data will be reanalyzed on the transformed scale. Results will be reported with p-values associated with the F-test for each contrast and the corresponding mean treatment differences with two-sided 95% confidence intervals. All tests of significance will be two-tailed at the 0.05 level.

Estimating the contrasts within the repeated measures framework will provide treatment comparisons that are robust to subject dropout bias as long as the dropout pattern is missing at random²⁷. Data are missing at random whenever the "missingness" mechanism is a function of observable relationships among the nonmissing responses and covariates. Using the methods of Ma et al.²⁸, we will evaluate the MAR assumption in the data prior to implementing the MMRM analysis. If the MAR assumption fails, we will consider more robust alternatives (e.g., pattern mixture modeling)²⁹.

A number of studies have shown RMANCOVA to be superior to analyses of completers or of data with LOCF imputations³⁰. Nonetheless, we will conduct 2 related sensitivity analyses: (1) replace the missing week-52 values with the corresponding nonmissing week 36 values of each subject, dropping anyone who is missing both week-36 and week-52 and perform the ANCOVA as currently specified; (2) include only the completers in the ANCOVA analysis (i.e., exclude all dropouts). The sensitivity analyses will be included as additional secondary analyses.

13.2.2 Secondary Clinical Endpoints

The secondary endpoints are defined in Protocol section 1.5.

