The protocol defines 28 secondary clinical endpoints. The endpoints are to be computed and summarized by treatment and, in a few cases, by day/week and treatment. With the exception of specific AEs and lab parameters, proportions or means will be estimated for each treatment arm and tested for treatment differences through the use of a statistical model. The particular model to be used depends on the scale of measurement of the endpoint. The accompanying table lists each endpoint and its measurement scale (continuous, dichotomous, and ordinal). All tests of significance in all analyses will be made at the 0.05 level.

Dichotomous measures of prevalence and incidence will be analyzed with log-binomial regression models, wherein treatment effects will be estimated as relative risk ratios; the reference group will be the tacrolimus-thymoglobulin subjects. The log-binomial model (rather than logistic regression) is applied for prevalence and incidence analyses because model-based estimates of relative risk (RR) are both more desirable and appropriate for non-Poisson events that are expected to occur more commonly than in 10% of the cases. In such cases, logistic regression-based odds ratio (OR) estimates are poor estimators of the relative risk³¹,³²,³³,³⁴. It may be appropriate to treat some of the dichotomous outcomes as censored data; if this is the case, we will obtain RR estimates by fitting Cox regression models to the data³⁵.

The single ordinal secondary outcome variable (Banff cell-mediated AR score) will be analyzed in a proportional odds model³⁶ which may include additional covariates and interaction terms, as appropriate.

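### Section 13.2.1 tests the primary week-52 eGFR contrast at two-sided 0.05, section 13.3 also labels a p-value below 0.10 significant, and nothing says which level decides

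*Combined protocol and SAP*

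**What the plan says.** Section 13.2.1, on the primary endpoint, sets one level: "All tests of significance will be two-tailed at the 0.05 level". Results are to be given as p-values and "mean treatment differences with two-sided 95% confidence intervals". Section 13.2.2 opens with a similar rule, "All tests of significance in all analyses will be made at the 0.05 level", although it stands under the secondary endpoints.

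Section 13.3 then works with two levels for the primary endpoint. Table 11 is introduced as the smallest differences "we will be able to declare significantly different, with 80% power and Type I error rates of 0.05 and 0.10". The text below the table says the study is powered at both levels and gives a reporting rule: "we will report a p-value as significant at the 0.10 level if it is less than 0.10", with a parallel clause for 0.05. It closes: "As previously stated, all secondary endpoint analyses will be performed at the 0.05 level".

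No section ranks the two levels or calls the 0.10 level supportive or exploratory. Sections 13.5.1 and 13.7 mention a SAP. Section 13.5.1 defers only the presentation of baseline data to it, and neither section defers the primary significance level.

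**The concern.** The same contrast has two thresholds. A p-value below 0.05 meets both and a p-value of 0.10 or more meets neither, so the trouble is confined to results in between. There, section 13.2.1 gives a non-significant test and section 13.3 gives a result labelled significant, at a level it names. The plan does not say whether such a result supports the hypothesis of superior renal function in section 1.1.

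Because section 13.3 restates 0.05 for the secondary endpoints alone, a reader can take the primary endpoint as a deliberate exception to 0.05. Another reader can take section 13.2.1 as governing. At stake is whether the trial's main claim can be made on a p-value of, say, 0.07, and whether the false-positive rate behind that claim is 5% or 10%.

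**Working it through.** **Inputs.** From section 13.3: 30 subjects per arm; standard deviations (SD) 16, 20 and 24; 80% power; alpha 0.05 and 0.10; detectable differences 12.0, 15.0 and 18.0 (alpha 0.05) and 10.5, 13.0 and 16.0 (alpha 0.10). From section 13.2.1: two-sided 0.05 and a 95% interval. The model here is an unadjusted two-sample t-test with all 30 per arm analysed. The planned repeated-measures model would supply a different standard error.

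**1. Reproduce Table 11.** SE = SD × √(2/30), which gives 4.131, 5.164 and 6.197. With df = 58, the two-sided critical values are t = 2.0017 at 0.05 and 1.6716 at 0.10. The differences that give 80% power by the noncentral t distribution are:

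| SD | alpha 0.05: exact (Table 11) | alpha 0.10: exact (Table 11) |
|---|---|---|
| 16 | 11.77 (12.0) | 10.39 (10.5) |
| 20 | 14.71 (15.0) | 12.99 (13.0) |
| 24 | 17.65 (18.0) | 15.59 (16.0) |

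Every entry is the exact value rounded up, so the table is right for each labelled alpha. Read as one-sided tests, the table's differences would have about 89% to 90% power, which does not match the stated 80%. The 0.10 in section 13.3 is therefore a two-sided 0.10, a looser criterion than that of section 13.2.1.

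**2. Where the two sections part.** They disagree when the estimate lies between 1.67 and 2.00 standard errors (1.64 to 1.96 in large samples). In eGFR units the bounds are t × SE. The last column is the lower 95% limit when p is just below 0.10, (1.6716 − 2.0017) × SE:

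| SD | from (p = 0.10) | to (p = 0.05) | lower 95% limit |
|---|---|---|---|
| 16 | 6.91 | 8.27 | −1.36 |
| 20 | 8.63 | 10.34 | −1.71 |
| 24 | 10.36 | 12.40 | −2.05 |

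Example: SD 20 and p = 0.07 give a difference of 9.5, a 95% interval of −0.8 to 19.9 and a 90% interval of 0.9 to 18.2. The plan would print a significance label next to an interval that contains zero.

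**3. How often.** With no true difference, p falls below 0.10 in 10% of trials (5% in favour of belatacept) and below 0.05 in 5% (2.5%). At true differences of 12, 15 and 18, each 0.75 SD, power is 81.5% at 0.05 and 89.0% at 0.10, so 89.0% − 81.5% = 7.5% of trials fall in the zone.

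**4. If 0.05 alone decides.** The 0.05 rows of Table 11 stand. At the 0.10-row differences of 10.5, 13.0 and 16.0, power is 70.5%, 69.7% and 71.9%, short of the 80% quoted.

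**The case against.** The strongest reply is that section 13.2.1 fixes the test and section 13.3 only grades the p-value in the report. Each label names its own level, both were set in advance, and the p-value, the difference and the 95% interval are all to be reported, so nothing is hidden. A 10% rate of results significant at the 0.10 level is true by definition, and becomes a type I error for the trial only if 0.10 is taken as success. In a 60-subject phase II trial with sample size fixed beforehand, a 0.10 level can be defended.

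Most of this is fair. The labels are truthful, and a phase II trial may use 0.10. But the grading reading is not forced. Section 13.3 ties both levels to what the study can declare different and to how it was powered. Disclosing two levels in advance does not tell the reader which one answers the primary question.

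Three limits stand:

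- The eGFR zones are illustrative. They do not carry over to a repeated-measures model with another standard error or to a log-scale reanalysis, and fewer degrees of freedom would raise the bounds slightly.
- A SAP outside the supplied text may already rank the levels.
- The amendment that halted further tacrolimus withdrawal affects how the week-52 contrast is read, whatever the alpha.

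**Conclusion.** The concern holds: the supplied text gives two thresholds for one primary test and does not rank them. It bites only for 0.05 ≤ p < 0.10. That is 5% of trials under no effect (10% − 5%) and 7.5% at true differences of 12, 15 or 18 for SDs of 16, 20 or 24. In that range the plan, followed as written, attaches a significance label to a result its own planned test calls non-significant.

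The statement about p-values does not depend on the model. The eGFR figures assume an unadjusted t-test with 30 analysed per arm. Neither the arithmetic of Table 11 nor the sample size is at fault. The point should be fixed, because it concerns the decision rule for the primary endpoint. Confidence is high that the supplied text lacks a ranking; whether a separate SAP contains one cannot be seen from here.

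**What to change.** State in sections 13.2.1 and 13.3 that two-sided 0.05 is the single deciding level for the primary endpoint. Section 13.2.1 already sets that level and pairs it with a 95% interval, and section 13.2.2 points the same way. In section 13.3, either delete the 0.10 reporting sentence or mark it as descriptive, with no bearing on the primary hypothesis. Note on Table 11 that the 0.10 rows show design sensitivity, so that 12, 15 and 18 are the detectable differences for the deciding test.

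The change must carry a date relative to database lock. Section 10.4.1 says analyses "will be blinded with respect to treatment prior to end-of-study database lock", apart from safety reviews by the DSMB. The amendment text at the front lets subjects receive study belatacept "until study completion on August 31, 2016". Neither shows whether lock has occurred. If the change comes after lock, it should be disclosed as such.

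The cost is wording only, with no change to sample size, data or conduct. The price is that the plan can quote only the less favourable detectable differences, and a p-value from 0.05 to below 0.10 could no longer count as a significant primary result.

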13.4 Safety Analyses

All adverse events (AEs) and serious adverse events (SAEs) will be classified by body system and preferred term according to the *Medical Dictionary for Regulatory Activities* (MedDRA). AEs and SAEs will be summarized as the frequency of each event by treatment group.

Frequency tables by treatment group and category of event (e.g., serious, related to study therapy, causing the discontinuation of study therapy) and by NCI-CTCAE grade will be presented. Selected laboratory values will also be summarized by treatment group using the mean and standard deviation of the change from baseline at scheduled visits.

13.5 Demographic Data

13.5.1 **Baseline Characteristics and Demographics**

Summary descriptive statistics for baseline and demographic characteristics will be provided for all enrolled participants. Demographic data will include age, race, sex, body weight, and height; these data will be presented in the following manner:

• Continuous data (i.e., age, body weight, and height) will be summarized descriptively by mean, standard deviation, median, and range.

• Categorical data (i.e., sex and race) will be presented as enumerations and percentages.

Statistical presentation for baseline and demographic characteristics will be further defined in the statistical analysis plan (SAP).

13.5.2 Medical History

Medical history will be collected, including the existence of current signs and symptoms and clinical significance for each body system.

13.6 Interim Analyses

No interim analyses are planned for this study. Unspecified interim analyses are only conducted if they will not adversely affect the integrity of the study or for safety reasons.

13.7 Reporting Deviations from Original Statistical Plan

The final study analysis will report the results of the original SAP. Any additional analyses will be identified as ad hoc. Clinical study report will be prepared and submitted to the health authority as specified in the FDA Guideline for Industry - Structure and Content of Clinical Study Reports - ICH E3 July 1996.

13.8 Final Study Analysis

The final study analysis will report the results of the SAP. Any additional analyses will be identified as ad hoc. A final study report will be prepared summarizing the results of analyses of the primary and secondary clinical endpoints and the analyses associated with the 12 mechanistic hypotheses.

14 SOURCE DATA

14.1 Source Data

All study data should be verifiable by source documentation. Most often this will be present in the patient's medical record. Except in rare instances, study documents (CRFs and data collection tools) are not source documents. "Shadow charts"-duplications of material from the medical record are not source documents.

14.2 Access to Source Data

The responsibilities of the study sponsor require that they and their representatives as well as the health authorities have access to (and may when required by applicable law copy) source documents Unless required by the laws that permit copying of records, only the coded identity associated with documents or with other participant data may be copied (and all personally identifying information must be obscured). Authorized representatives as noted above are bound to maintain the strict confidentiality of medical and research information that is linked to identified individuals.

15 QUALITY CONTROL AND QUALITY ASSURANCE

The investigator is required to keep accurate records to ensure that the conduct of the study is fully documented.

The sponsor is responsible for regularly reviewing the conduct of the trial, for verifying adherence to the protocol, and for confirming the completeness, consistency, and accuracy of all documented data.

15.1 Data Handling

The investigator is required to ensure that all CRFs are completed for every participant entered in the trial. All elements of data entry (i.e., time, date, verbatim text, and the name of the person performing the data entry) will be recorded with an audit trail to allow all data changes in the database to be monitored and maintained in accordance with federal regulations.

16 ETHICAL CONSIDERATIONS AND COMPLIANCE WITH GOOD CLINICAL PRACTICE

16.1 Statement of Compliance

This clinical study will be conducted using good clinical practice (GCP), as delineated in *Guidance for Industry: E6 Good Clinical Practice Consolidated Guidance* and according to the criteria specified in this study protocol. Before study initiation, the protocol and the informed consent documents will be reviewed and approved by an appropriate EC or IRB. Any amendments to the protocol or to the consent materials must also be approved before they are implemented.

16.2 Informed Consent Process

The consent process provides information about the study to a prospective participant and allows adequate time for review and discussion prior to their decision. The principal investigator or designee listed on the FDA 1572 will review the consent and answer questions. The prospective participant will be told that being in the trial is voluntary and that he or she may withdraw from the study at any time, for any reason. All participants (or their legally acceptable representative) must read, sign, and date a consent form before undergoing any study procedures. Consent materials must be presented in participants' primary language. A copy of the signed consent form must be given to the participant. The consent process is ongoing. The consent form must be revised when important new safety information is available, the protocol is amended, and/or new information becomes available that may affect participation in the study.

16.3 Privacy and Confidentiality

A participant's privacy and confidentiality will be respected throughout the study. Each participant will be assigned a unique identification number and these numbers rather than names will be used to collect, store, and report participant information. Site personnel should not transmit documents containing personal health identifiers (PHI) to the study sponsor or their representatives.

17 PUBLICATION POLICY

The Clinical Trials in Organ Transplantation (CTOT) policy on the publication of study results will apply to this trial. The CTOT Publication Policy is located on the CTOT website at www.ctotstudies.org.

Appendix 1: Schedule of Events – Pre-Transplant to Day 4 Post-Transplant (Visit 1)

Screening Assessments	Window
 Blood Type (A, B, O), Rh Factor HLA Typing (Class I: A, B, C, Class II: DR, DP, DQ) Peak PRA, Current PRA or cPRA (within 12 months prior to transplant), Crossmatch Hepatitis B, Hepatitis C, and HIV test results Last reported CMV (IgG, IgM and/or total CMV Ab) and EBV testing (IgG, IgM) Tuberculosis testing (within 12 months prior to transplant). If documentation is not present at the time of transplant, and the subject does not have any risk factors for TB, a TB-specific interferon gamma release assay (IGRA) may be performed. 	Retrospective data collection, no time limits unless specified. Repeat only if not available.
 Informed Consent and Assessment of Eligibility Demographics Medical History, Physical exam (BP, Pulse, Temperature, Respiration, Weight) Concomitant Medications Local Labs: Serum Pregnancy Test, Hematology Panel (CBC, differential, platelets), Chemistry 12-Panel / CKD-EPI equation, MDRD 4 variable, Serum Amylase, Serum Lipase, Fasting Lipid Panel (Total, HDL, LDL, Triglycerides), Hemoglobin A1c, Urinalysis 	Within 30 days prior to transplant, until time of transplant.
 Flow Cytometry (20mL blood in Cyto-Chex Tube) Intracellular Cytokine Staining – Viral Phenotyping (32mL blood in CPT Tube) Markers of Autoimmunity – PBMC (30mL blood in Green-top Tube) Markers of Autoimmunity – serum (5mL blood in Red-top Vacutainer) Gene Expression, mRNA profiling in blood (2.5 mL blood in PAXgene RNA tube) Cytokines and Growth Factors- serum (7mL blood in Red-Top Vacutainer) Serum Proteins – CTGF, TGFbeta (4.5mL blood in CTAD) Urine Proteins – CTGF, TGFbeta (supernatant) Gene Expression, mRNA profiling in urine (urine pellet) Non-HLA Ab, Anti-HLA Ab, DSA (5mL blood in Red-top Vacutainer) Genomics- gene polymorphisms (4mL in Lavender-top EDTA Vacutainer) Viral Monitoring by PCR (CMV, BKV, JCV, HHV6, HHV7) and Viral Assay Development (HHV3- varicella zoster, HHV6- roseola, HHV7- cofactor CMV, polyoma JC, WC, KI).(plasma from ICS sample) 	Within 48 hours prior to transplant
 Randomization (RhoRand System) Assessment of Events: AE/SAE Solumedrol®(Methylprednisone) : 500mg – Intraoperatively Thymoglobulin® (Anti-thymocyte Globulin – Rabbit) Prograf® (tacrolimus) CellCept® (mycophenolate mofetil) 	Day of Transplant
 Methylprednisolone 250 mg Thymoglobulin® (Anti-thymocyte Globulin – Rabbit) 	Day 1 Post-Transplant
 Methylprednisolone 125 mg Thymoglobulin® (Anti-thymocyte Globulin – Rabbit) 	Day 2 Post-Transplant
 Methylprednisolone 60mg Thymoglobulin® (Anti-thymocyte Globulin – Rabbit) 	Day 3 Post-Transplant
Methylprednisolone 30mg	Day 4 Post-Transplant

